In neonatology, the use of probiotics is becoming increasingly widespread as a preventive measure against necrotising enterocolitis and late-onset sepsis. Based on theories about the interaction of probiotics with the immune system, it may be that the use of probiotics in this population may offer other medium- to long-term benefits in inflammatory diseases.

OBJETIVES

The main objectives are as follows:

1. To evaluate the association between nutritional factors in the neonatal period and atopic dermatitis, in relation to prevention.
2. To assess whether the use of breastfeeding and probiotic supplementation in very low birth weight infants as prophylaxis for necrotising enterocolitis is associated with a decrease in atopic dermatitis at preschool and school age.
3. To determine probiotic strains that offer benefits in reducing the occurrence of atopic disease.

The secondary objectives are set out below:

1. To assess whether the use of breast milk (both fresh and donated) offers a synergistic effect, when combined with probiotics, in the reduction of atopic dermatitis.
2. Impact of caloric and protein intake in very low birth weight infants on the development of atopic dermatitis later in life.

DESIGN AND METHODS

Observational retrospective cohort study in very low birth weight infants, <1500 grams and/or < 32 weeks, hospitalised in the Neonatal Intensive Care Unit at the Hospital Universitario Clínico San Cecilio between January 2009 and December 2021.

Enteral and parenteral nutritional data, type of feeding (fresh and/or thawed breast milk, donated breast milk or formula), probiotic administration and strain administered are recorded. Parental permission is available for all patients included in the study.

Inclusion and exclusion criteria:

All patients hospitalised in the Neonatal Intensive Care Unit with < 1500 grams birth weight and/or < 32 weeks at birth during the indicated time period. Deceased patients, incomplete or unavailable medical history and patients with severe congenital diseases are excluded.

Nutritional management:

The unit's nutrition and fluid management protocol, both enteral and parenteral, follows the recommendations of the Nutrition and Metabolism Group of the Spanish Society of Neonatology. Daily fluid (ml/kg/day), carbohydrate (mg/kg/min), protein (g/kg/day), lipid (g/kg/day) and calorie (kcal/day) intakes are calculated.

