Given the characteristics of this group of patients, as described above, nutritional needs are often met with parenteral nutrition combined or not with enteral feeding. The objective is to cover the minimum needs to guarantee adequate growth and development of the newborn.

In relation to enteral nutrition, the first choice is fresh breast milk, sometimes it is necessary to freeze it for preservation, and it is thawed prior to use. In cases of unavailability, with parental consent, donated milk that has been pasteurised according to Holder's method is administered, or failing that, formula for premature infants.

Fortification with maternal or donated milk is started from one week of life, once water intake of at least 80 ml/kg/day has been achieved.

In our unit, the use of probiotics was initiated in December 2013 as a preventive measure against the development of necrotising enterocolitis. Two strains were available: *Lactobacillus Rhamnosus GG* and the combination of *Lactobacillus acidophilus* + *Lactobacillus bifidum*. The choice of the type administered depended on the preference of the responsible paediatrician. The probiotic was introduced after initiation of satisfactory enteral nutrition and continued until 35 weeks postnatal or until discharge from the unit.

Atopy registry:

Atopy is a state of abnormal hypersensitivity to exposure or contact with non-pathogenic antigens. We record a history of atopic dermatitis and first-degree family history.

STATISTICAL CONSIDERATIONS

In our study we have two types of descriptive variables: continuous variables and categorical variables.

- For continuous variables we will use the median and interquartile range, using the Mann-Whitney test for comparison.
- For categorical variables, distribution frequencies will be used, analysing them by means of Chi-square.

In order to study more than one variable on the desired effect, multivariate logistic regression analysis will be used.

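### If siblings are in the cohort, the planned logistic regression and Chi-square slightly overstate precision for probiotic receipt and milk type, because infants are treated as independent

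*Combined protocol and SAP*

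**What the plan says.** Under Inclusion and exclusion criteria the cohort is "All patients hospitalised in the Neonatal Intensive Care Unit with < 1500 grams birth weight and/or < 32 weeks at birth", admitted "between January 2009 and December 2021". The only removals are these: "Deceased patients, incomplete or unavailable medical history and patients with severe congenital diseases are excluded". Twins, higher multiples and later siblings are therefore eligible, and nothing limits a family to one infant.

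Statistical Considerations names three methods: Mann-Whitney for continuous variables, Chi-square for categorical variables and, for joint effects, "In order to study more than one variable on the desired effect, multivariate logistic regression analysis will be used". Neither section mentions family, clustering, GEE, random effects or robust variance.

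Main objective 2 opens "To assess whether the use of breastfeeding and probiotic supplementation in very low birth weight infants" and asks whether these exposures go with less atopic dermatitis. On the exposures, Nutritional management states "In our unit, the use of probiotics was initiated in December 2013" and "The probiotic was introduced after initiation of satisfactory enteral nutrition". Design and Methods adds that "probiotic administration and strain administered are recorded", which makes receipt a per-infant variable. Milk type follows the availability of the mother's own milk, then parental consent to donor milk, then formula. The Atopy registry paragraph records first-degree family history, but the plan does not say that this enters the model.

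**The concern.** Very preterm and very low birth weight cohorts can be expected to contain sibling sets, although the documents do not say how many are in this one. When two infants share a mother, their outcomes may be alike. If their exposure is alike too, the pair carries less information about that exposure than two unrelated infants. A model that assumes independence then reports intervals that are too narrow and p-values that are too small.

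Both exposures in main objective 2 are candidates. Milk type depends partly on the mother's supply and the parents' consent. Probiotic receipt was impossible for anyone born and discharged before December 2013, so co-twins from that period share non-receipt. At stake is the reading of a borderline result for the plan's main question, not the direction or size of the association.

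**Working it through.** The plan states no sample size, power, significance level or event rate, so there is no figure of its own to reproduce. The check asks how large the effect could be.

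**Inputs from the documents.** January 2009 to November 2013 is 59 months and December 2013 to December 2021 is 97 months, 156 in total. The fraction of the window in which probiotics were available is q = 97/156 = 0.622.

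**Assumed inputs (not in the documents).** Share of infants in twin pairs f = 20–40%; within-pair outcome correlation ρy = 0.2–0.6; within-pair exposure correlation ρx = 0.5 for milk; later probiotic receipt r = 60, 75 or 90%; even admissions over time; two-sided 5% test.

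**Step 1: probiotic correlation implied by the start date.** Suppose receipt after December 2013 is independent between co-twins. With no adjustment for period, the pooled within-pair correlation is ρx = r(1 − q)/(1 − qr):
- r = 0.60: 0.60 × 0.378 / (1 − 0.373) = 0.36
- r = 0.75: 0.75 × 0.378 / (1 − 0.466) = 0.53
- r = 0.90: 0.90 × 0.378 / (1 − 0.560) = 0.77

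If the model adjusts for before/after December 2013, this component disappears.

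**Step 2: design effect.** DEFF = 1 + f × ρy × ρx. The naive standard error is too small by 1 − 1/√DEFF. The large-sample error rate is 2(1 − Φ(1.96/√DEFF)). The naive p-value that corresponds to a corrected 0.05 is 2(1 − Φ(1.96√DEFF)).

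| Case | DEFF | SE too small by | Large-sample error | Naive p needed |
|---|---|---|---|---|
| ρx = 0.5, low (f 0.2, ρy 0.2) | 1.02 | 1% | 5.2% | 0.048 |
| ρx = 0.5, high (f 0.4, ρy 0.6) | 1.12 | 6% | 6.4% | 0.038 |
| ρx = 1, high (upper bound) | 1.24 | 10% | 7.8% | 0.029 |

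With smaller inputs (f = 0.1, ρy = 0.1, ρx = 0.5) DEFF is 1.005 and the standard errors differ by 0.2%, so the range effectively starts at zero. If the exclusions keep a random 80% of infants, the share in pairs falls to 16–32%, DEFF at ρx = 0.5 to 1.016–1.096, and error to 5.2–6.1%. If every pair is discordant on exposure, ρx = −1, DEFF is 0.76–0.96 and error is 2.5–4.5%: the naive analysis is then conservative.

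**Step 3: simulation of the unadjusted logistic Wald test under the null.** At N = 400 and 20% risk (both assumed), with (f, ρy) = (20%, 0.2), (40%, 0.4) and (40%, 0.6), naive error was 5.1, 6.0 and 6.1% at 75% later receipt. Over 60–90% receipt it ran from 5.0 to 7.0%, the top value occurring only at 90% receipt with the highest settings. A separate run at the same N and risk gave 5.2–6.6%. Mother-clustered standard errors gave 4.6–5.2% in all 27 scenarios tried at N = 400.

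**Step 4: sparser data, 75% receipt, 10% risk, lowest and highest settings.** Naive Wald error was 4.4 and 5.3% at N = 200, 3.7 and 5.0% at N = 150, and 2.6 and 3.5% at N = 100. The Wald test is conservative there. At the highest setting clustering still raised the error above its no-sibling level, but the total need not pass 5%.

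**The case against.** The strongest reply is that almost nothing here is anchored. Apart from the dates, every input is assumed, and the borderline argument uses a 5% threshold that the plan never states. This stands. The size can be given only as a range, and its lower end is practically nil.

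Second, the error rates depend on a sample size and event rate that the documents do not give. A reader might infer that the planned tests necessarily exceed 5%. They need not: in sparse data the logistic Wald test stayed below it. What carries over is the comparison of naive with clustered standard errors.

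Third, much of the probiotic correlation is a by-product of the December 2013 start, and a period term would remove it. This also stands. The plan specifies no such term, however, and any sharing of later receipt or of milk type would remain. Calendar confounding of the odds ratio is a separate and probably larger question.

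Fourth, a reader might infer that co-twins always had the same probiotic exposure. The documents do not support that. Receipt is recorded per infant, and the sentence on satisfactory enteral nutrition describes when the product was introduced, which can differ between co-twins.

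Adjustment for family history would reduce the problem without reliably removing it. With 75% later receipt and an assumed 30% prevalence of such history, simulated error was 5.1–6.3% if history is a moderate predictor and 4.8–5.8% if it is a strong one.

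**Conclusion.** The point holds as a conditional and modest one. The eligibility text admits siblings, and the named tests ignore them. If sibling sets are present, and outcome and exposure are both positively correlated within families, naive standard errors for probiotic receipt and milk type are about 1–6% too small at exposure correlation 0.5, and up to about 10% if exposure is fully shared. This assumes 20–40% of infants in pairs and outcome correlation 0.2–0.6. Actual type I error is about 5–6.6% at N = 400 and 20% risk (7.0% in the most extreme probiotic setting), and can stay under 5% for the Wald test in sparse data.

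Two wider readings go too far. One is that the odds ratios are biased: this mechanism acts on precision and does not materially move the estimates. The other is that every p-value in the plan is compromised. The milk–probiotic interaction in secondary objective 1 is affected less (simulated 5.1–5.8% at exposure correlations 0.53 and 0.5). Strain and individual caloric or protein intake need not be affected, and Mann-Whitney was not examined. Priority: minor.

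**What to change.** Add a mother or pregnancy identifier to the dataset, and report the number of sibling sets and the number of infants in them. If there are any, fit the logistic model as planned with standard errors clustered on mother, and treat the unadjusted Chi-square p-values for probiotic receipt and milk type as descriptive. Mann-Whitney comparisons and the other Chi-square comparisons need no change on this ground. If there are no sibling sets, nothing changes.

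The cost is one extra field and one software option. The downside is slightly wider intervals: about 1–6% at exposure correlation 0.5 (√1.02 = 1.01, √1.12 = 1.06), and up to 11% if exposure is fully shared (√1.24 = 1.11).
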